### **Funding**

Couples in the UNiTY study will not have to pay for the three cycles of IUI. Those eligible for IVF NHS funding will discuss this with the research team prior to randomisation. They will know the parameters of their funding and whether the trial will impact this. This will inform the couple's decision to take part in the trial.

## 7.1.2. IVF strategy

### **Ovarian stimulation**

The IVF cycle will be carried out as per the fertility clinic's normal practice. The IVF cycle type (agonist or antagonist), medication used, and monitoring schedule will be determined by the individual clinics.

#### **Embryo transfer**

Single embryo transfers (fresh or frozen) will be standard practice.

### **Further transfers**

Couples who use frozen embryos from their cycle in subsequent cycles do so outside of the main trial intervention, but outcomes will be collected up to a maximum of 25 months post-randomisation (see section 8).

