# **Arms**

Intervention: Three cycles of letrozole stimulated Intra Uterine Insemination (IUI).

Control: One cycle of In-Vitro Fertilisation (IVF) with standard ovarian stimulation and first fresh or frozen embryo transfer.

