# 1.1.4 Research trial proposed

There is a great deal of uncertainty regarding IUI versus IVF. Stimulated IUI, if effective, is potentially an attractive option for many couples and for ICBs because it is lower risk, less invasive and possibly more cost effective.

The UNiTY trial is a multi-disciplinary, multi-centre randomised controlled trial (RCT) designed to answer the question of whether IUI is an effective and cost-effective alternative to IVF for UEI in an ethnically and socially diverse UK population. In line with the new Medical Research Council (MRC) (NIHR) framework for developing and evaluating complex interventions, UNiTY will assess feasibility, value for money, safety and patient acceptability throughout the process. The potentially unreliable result of semen analysis is a significant factor in defining UEI and therefore trial entry. Inter-centre quality assurance of sperm analysis therefore forms a cornerstone of our trial and is a necessity to allow for the diversity of practice across the UK.

The intervention is the policy of offering three cycles of letrozole-stimulated IUI and the comparator is the policy of offering one cycle of IVF with standard ovarian stimulation and the first fresh and / or frozen embryo transfer. We will initially assess outcomes 19 months post-randomisation, when we anticipate couples will have been treated with their first IVF cycle or three cycles of stimulated IUI and subsequent pregnancy outcomes obtained. As we expect all couples unsuccessful after three cycles of IUI will proceed to at least one cycle of IVF, we will also collect and assess this data up to 25 months post-randomisation (treatment with further IVF cycles in either group will be dependent on local policy, if further NHS funding is available in a locality to a couple this will also be recorded). Within all cycles in the IVF pathway, the number of surplus frozen embryos will be documented as this can clearly inform of potential cumulative pregnancy rates — which could later be followed-up in future investigations.

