#### 8.2. Main trial outcomes

#### 8.2.1. Primary outcome

The primary outcome is the live birth of a baby at ≥34 week's gestation, conceived within 270 days of randomisation (approximately 9 months). Date conceived is determined as date of egg collection for couples who have undergone fresh embryo IVF, date of embryo transfer minus the number of days of culture for couples who have undergone frozen embryo IVF, date of insemination for couples who have undergone IUI, and 14 days after the first day of the last period for couples who have conceived naturally.

In line with the evaluation of treatment policy, initial or subsequent pregnancies may be included within this timeframe. This outcome will be assessed at 19 months post-randomisation.

\_\_\_\_\_\_

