## Additional notes on Error! Reference source not found.

- Months 2-6 are an approximation for when couples will have the three cycles of IUI; this process may be longer.
- X Couples randomised to IUI but progress to IVF as part of clinical care. All couples randomised to IUI cannot progress to subsequent IVF treatment until 270 days (approximately 9 months) post randomisation.
- X to measure outcomes for all couples who conceive within 450 days of randomisation.
- X³- one Clinical Pregnancy Outcome CRF to be completed per positive pregnancy test.
- X- to be completed for each pregnancy conceived during the trial outside of IVF or IUI treatment.
- X one Post-Treatment CRF to be completed 8 weeks after treatment starts (defined as the first day of ovarian stimulation).
- The qualitative sub-studies will approach participants at the indicated timepoints, but their interviews will happen in the subsequent weeks.
- X- measured during the first treatment cycle of IUI and/or IVF. The ideal timepoint during a treatment cycle to collect these questionnaires is between the date of insemination and the date of the pregnancy test for couples undergoing IUI, and between the date of embryo transfer and the date of the pregnancy test for couples undergoing IVF.

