## 14.STATISTICAL CONSIDERATIONS

## 14.1. Sample size

The HFEA suggests that the primary outcome rate in the IVF group will be approximately 28% (1). To ensure the IUI group will be within a 10% margin of non-inferiority (i.e., no lower than 18%) with 90% power (one-sided alpha of 0.025, equivalent to a two-sided alpha of 0.05), the trial will require 942 participants (assuming a conservative 10% loss to follow-up).

A three IUI cycle rate of at least 18% (approximately 6.4% per-cycle) would deliver 64% of the live births of IVF for 46% of the total costs, justifying the 10% margin of non-inferiority from a commissioning or self-funding couple financial perspective (see Table 8*Table 8*). A success rate matching IVF (28%) would be for 44% of the total costs of IVF (see Table 9).

The margin of non-inferiority is also justifiable if we consider that many of those allocated to IUI who do not achieve live birth will go on to receive an IVF cycle provided by the NHS, even considering further interventions and the possibility of natural birth in the IVF policy group [MRC/NIHR framework, core element 1: context]. We will assess whether the initial IUI treatment policy is the superior approach in our medium-term assessment (25 months post-randomisation). For this assessment, we will have adequate (>80%) power to detect a 10% difference in live birth (≥34 weeks) rates (e.g., 45% vs 35%).

**Table 7:** Cost comparison, assuming a 10% margin of inferiority, between 3 cycles of IUI (assumed success rate per cycle of 6.4%) and 1 cycle of IVF (assumed success rate per cycle of 28%)

	IUI Cycle 1	IUI Cycle 2	IUI Cycle 3	IVF Cycle 1
Number of couples	100.0	89.6	80.4	100.0
Expected live births	6.4	6.0	5.6	28.0
		Total live births	18.0	28.0
		Number of cycles	281.2	100.0
	Cost per cycl		£605.33	£3,682.00
	Total cost		£170,225.54	£368,200.00
	Cost per live birth		£9,458.33	£13,150.00

**Table 8:** Cost comparison, assuming a 0% margin of inferiority, between 3 cycles of IUI (assumed success rate per cycle of 10.36%) and 1 cycle of IVF (assumed success rate per cycle of 28%)

	IUI Cycle 1	IUI Cycle 2	IUI Cycle 3	IVF Cycle 1
Number of couples	100.0	89.6	80.4	100.0
Expected live births	10.4	9.3	8.3	28.0
		Total live births	28.0	28.0
		Number of cycles	270	100.0
		Cost per cycle	£605.33	£3,682.00
	Total cost		£163,435.94	£368,200.00
	Cost per live birth		£5,842.99	£13,150.00

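### The 28% IVF rate behind the sample size and margin is a one-cycle rate while the primary outcome counts every conception to day 270, and the per-protocol/CACE row that should isolate one cycle sorts couples by whether they conceived

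*Protocol*

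**What the plan says.** Tables are cited here by their captions; some in-text references are one number higher.

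- **Comparator.** The trial summary (Arms) gives "One cycle of In-Vitro Fertilisation (IVF) with standard ovarian stimulation and first fresh or frozen embryo transfer". Section 1.1.4 gives "one cycle of IVF with standard ovarian stimulation and the first fresh and / or frozen embryo transfer". Section 7.1.2 (Further transfers) says: "Couples who use frozen embryos from their cycle in subsequent cycles do so outside of the main trial intervention". Section 7.6 treats an IVF couple as adherent if they had one cycle and no fertility treatment after it.
- **Primary outcome.** Section 8.2.1 counts a live birth at 34 weeks or later conceived within 270 days, and "initial or subsequent pregnancies may be included within this timeframe". The primary intention-to-treat row of Table 9 includes, in both arms, couples who conceived after further IUI, IVF or frozen transfer.
- **Sample size and margin.** Section 14.1 expects about 28% in the IVF group, and the captions of Tables 7 and 8 attach that figure to "1 cycle of IVF (assumed success rate per cycle of 28" per cent). The 18% floor and the cost argument (64% of the births for 46% of the cost) follow from it.
- **Supportive analyses.** In Table 9 the per-protocol/CACE row at 270 days says No to couples who conceived with further intervention. It says Yes to couples who did not conceive after at least one IVF (IVF arm) or at least three cycles (IUI arm).
- **IVF in the IUI arm.** The notes to the schedule of assessments (section 9.1) state: "All couples randomised to IUI cannot progress to subsequent IVF treatment until 270 days". Section 7.1.1 offers IVF after three IUI cycles or at 270 days. Section 15.2 says not before eight months.

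**The concern.** The sample size and the primary outcome appear to describe different quantities. One is the yield of a single IVF cycle; the other is everything conceived in nine months by couples who start with IVF. An IVF couple whose first transfer fails early may have time before day 270 for a frozen transfer, or for a second cycle where funded. If the schedule note holds, IUI couples have no access to IVF in that window. The 270-day IVF rate could then sit above 28% for reasons unrelated to the first cycle, while the margin, floor and power are still read off 28%.

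The analysis that ought to show the one-cycle contrast is the per-protocol/CACE analysis. If it sorts couples by whether they conceived, it does not estimate that contrast. A failed non-inferiority result could then not be traced either to weak IUI or to extra transfers in the IVF arm.

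**Working it through.** **1. Reproduce the plan's figure.** Inputs from section 14.1: 28% in both arms, margin 10 points, one-sided alpha 0.025, power 90%, loss 10%.

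n per arm = (1.960 + 1.282)² × (2 × 0.28 × 0.72) / 0.10² = 10.507 × 0.4032 / 0.01 = 423.7, so 424. Dividing by 0.9: 423.7 / 0.9 = 470.7, so 471 per arm and 942 in total. Rounding to 424 before inflating gives 472 per arm, or 944. The stated 942 is reproduced, so the 28% input is the only question.

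**2. Raise the IVF arm only.** Power = Φ[(0.10 − (p_IVF − 0.28)) / SE − 1.96], with SE = √[(p_IVF(1 − p_IVF) + 0.28 × 0.72) / 424]. Worked at 30%: SE = √[(0.2100 + 0.2016) / 424] = 0.0312; 0.08 / 0.0312 − 1.96 = 0.61; power 73%. The implied floor is p_IVF minus 10 points.

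| 270-day IVF rate (IUI 28%) | Power | Implied IUI floor |
|---|---|---|
| 28% | 90% | 18% |
| 29% | 83% | 19% |
| 30% | 73% | 20% |
| 32% | 48% | 22% |

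**3. What could move the rate that far.** The protocol gives no figure, so this is assumption. If a share u of the 72% without success has one more transfer by day 270, succeeding with probability s, the rate is 28% + 72% × u × s. For u = 10%, s = 20%: 28 + 1.4 = 29.4%, power about 79%. For u = 20%, s = 28%: 28 + 4.0 = 32.0%, power about 48%.

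**4. Raise both arms equally.** At 30% in each arm power is 89%; at 35% in each arm it is 86%. The loss therefore depends on the gap between arms, not on the level.

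**5. The per-protocol/CACE row.** Take 100 IVF couples who all start IVF: 28 succeed from the first transfer, 4 only from a later transfer, and 68 do not succeed. For simplicity treat conceiving and succeeding as the same. Table 9 drops the 4 and keeps the 68, including any who had later transfers that failed. The rate is 28 / (28 + 68) = 28/96 = 29.2%, whereas the one-cycle rate is 28/100 = 28%. Section 7.6 would exclude every couple with further treatment, whether or not it worked. Table 9 excludes only those for whom it worked. In the CACE analysis the same couples are labelled adherent or not according to their outcome.

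**The case against.** A reader might infer that the trial does not test its own question. The text does not support that. The primary objective (section 2.2.1) compares policies of offering treatment. Section 1.1.4 says "the comparator is the policy of offering one cycle of IVF with standard ovarian stimulation". Section 1.2.4 (choice of primary outcome), section 7.6 and section 8.2.1 all say that treatment policy is what is evaluated. Counting later treatment follows from that choice. Section 14.1 also mentions further interventions in the IVF group when it defends the margin, although it puts no number on them.

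Other points on that side stand in part:

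- That the 270-day IVF rate will exceed 28% is not established. Couples who receive no intervention and cancelled cycles count as failures and pull the rate down, and the content of the source behind 28% cannot be checked here.
- The imbalance between arms rests on the schedule note. Sections 7.1.1 and 15.2 read differently, and Table 9 provides for further intervention in the IUI arm at 270 days. Any such conceptions would offset the effect.
- CACE keeps all randomised couples, so it is not true that no planned analysis does. Table 9's second footnote limits per-protocol to outcomes of the randomised intervention, which could be read as scoring later births as failures. But the row says No to those couples, so the table does not apply that reading, and adherence still turns on conception.
- Detail on scoring may sit in the statistical analysis plan. The conflict between Table 9 and section 7.6 is nevertheless fixed in the protocol itself.

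**Conclusion.** The treatment-policy primary analysis is sound. Two defects remain.

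(a) The 28%, the 18% floor and the cost comparison describe one IVF cycle, while the outcome is cumulative to day 270. If only the IVF arm rises, power falls from 90% to 83%, 73% and 48% at 29%, 30% and 32%. This assumes IUI at 28%, 424 analysed per arm and the unpooled normal approximation. How far the rate rises, if at all, is not in the protocol. If both arms rise together to 30-35%, little is lost. Extra IVF-arm births work against IUI, so the danger is a missed true non-inferiority, not a false claim of it. A reader might push the range higher and infer near-zero power. But at 38% against 28% the true difference equals the margin, and the 2.5% chance of success there is the type I error. For the policy question, failing would be the right result.

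(b) The per-protocol/CACE row at 270 days selects on outcome, contradicts section 7.6 and does not give the one-cycle contrast. The distortion is about one point in the example (29.2% against 28%).

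**What to change.** 1. Keep the treatment-policy analysis as primary and as the sole basis for the non-inferiority claim.
2. Add one supportive analysis of all randomised couples. Success is a live birth at 34 weeks or later, conceived by day 270 from the allocated treatment (the IVF cycle with whichever transfer or transfers are defined as allocated, or the first three IUI cycles) or naturally. Births from any other treatment score as not a success.
3. In Table 9, define adherence by treatment received, in line with section 7.6, and not by whether the couple conceived.
4. In section 14.1, label 28% as a one-cycle rate and show power and the implied floor over a stated range of 270-day policy rates.
5. Use one comparator wording in the trial summary and in sections 1.1.4, 7.1.2 and 7.6, stating whether a frozen transfer after a failed fresh one is allocated treatment.
6. Reconcile section 7.1.1, the notes in section 9.1 and section 15.2 on when IVF opens to the IUI arm.

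The cost is wording plus one supportive analysis. The IVF, Frozen Transfer and Non-trial treatment forms already record the treatments needed. The drawback is that the stated power will look less favourable.

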#### **Funding**

Couples eligible for NHS treatment will not have to pay for IVF in the trial. Self-funding couples will need to pay for treatment prior to randomisation to ensure they have sufficient funds. Self-funding couples will be reimbursed if not randomised to IVF.

### 7.2. Drug interaction or contraindications

# 7.2.1. Permitted medication(s)/intervention(s) (including rescue medication)

All standard medications associated with Medically Assisted Reproduction (newer term for assisted reproductive therapy) (MAR) ovarian stimulation will be permitted for the IVF cycle as it will depend on the Anti-Mullerian Hormone (AMH) level, or antral follicle count. The final stimulation dosage, medication, duration of stimulation and protocol employed will be recorded, as well as method of luteal support. For IUI, letrozole is the chosen medication with the duration of stimulation recorded, as well as method of luteal support if employed.

# 7.2.2. Concomitant medication(s)/intervention(s)

Both partners may be taking supplements, or concomitant medication as part of other routine treatment. Continuing or pausing these medications will be decided by the clinical team, and relevant concomitant medication will be recorded.

# 7.2.3. Prohibited medication(s)/intervention(s)

Prohibited medications would only be those of unwarranted / unknown effect in initial MAR treatment. This would include intralipid infusions and immunosuppressive treatment such as corticosteroids.

#### 7.3. Intervention modification or discontinuation.

All patients receiving off-protocol treatment will remain in the study. Data will continue to be collected from the couple until the end of their study duration. Any fertility treatment accessed by participants after completion of trial treatments is not considered a protocol deviation.

To minimise the multiple pregnancy risk, when more than 2 follicles >15mm are present at the time of HCG triggering, IUI should be withheld (17), this will be recorded in the trial as one of the three attempts as this again pragmatically reflects what would occur in current practice.

### 7.4. Continuation of intervention after the trial.

If couples do not have a live birth through the trial interventions, further treatment will be discussed with their clinical team outside of the trial.

# 7.5. Intervention supply and storage

All medications used within UNiTY are routine for the two different treatment arms. As such standard local protocols for supply and storage of drugs will be followed.

### 7.6. Adherence

The primary analysis will examine treatment policy (all randomised participants regardless of adherence to intervention), but further analysis will investigate the intervention effect within the population of adherent couples (see Section 14). For this purpose, the adherent population will be defined as receiving three cycles of IUI (or one or two cycles if pregnant from earlier cycles) with no further fertility treatment in the IUI strategy group and one cycle of IVF with no further fertility treatment in the IVF strategy group.

Adherence to intervention will be monitored via periodic data review performed by TMG, DMC and TSC.

# Definition of cancelled and complete treatment cycles

- IVF and IUI cycle cancellation if the partner providing eggs has had a stimulation injection, but the rest of the procedure was cancelled prior to egg collection (IVF), or insemination (IUI).
- Complete cycles if embryo transfer (IVF) or insemination (IUI) has taken place.

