#### 7.1.1. IUI strategy

#### **Ovarian stimulation**

IUI with the aromatase inhibitor letrozole will be commenced at a dose of 5mg (2 tablets) once daily from day 2 − day 6 after commencement of period. Follicular tracking will be according to local protocol, but this is usually commenced around day 10 − day 12 using transvaginal ultrasound. When at least one follicle reaches a diameter of ≥17mm, ovulation triggering using human chorionic gonadotrophins should be administered. This will ensure that IUI can be performed at a planned time convenient to the patient and staff. Luteal support will be provided according to local protocols.

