#### Insemination

Single insemination should be planned 24-40 hours post the ovulation trigger injection (33, 34). Patients will be advised to have 10-15 min bed rest after the insemination is performed (35). Protocols will be managed according to local policy to minimise the chance of multiple pregnancy. Where no policy exists (e.g. in clinics with no current IUI provision), the suggested policy will be that when more than 2 follicles >15mm are present at the time of HCG triggering, the cycle should be cancelled and the couple advised to refrain from unprotected intercourse.

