# Cancelled cycles and trial data

When cycles are cancelled it will be at the discretion and cost of the provider (treatment centre) as to whether a complimentary cycle is offered. Any replacement cycles will be recorded as non-trial treatments.

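### Section 7.6 defines a cancelled cycle by a stimulation injection, but IUI is stimulated with letrozole tablets, so an IUI cycle stopped before the hCG trigger is neither cancelled nor complete

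*Protocol*

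**What the plan says.** The definition is in section 7.6, under the heading on cancelled and complete cycles: "IVF and IUI cycle cancellation if the partner providing eggs has had a stimulation injection, but the rest of the procedure was cancelled" before egg collection (IVF) or insemination (IUI). A cycle is complete once embryo transfer or insemination has taken place. The next paragraph leaves it to the treatment centre, at its own cost, whether to offer a further cycle after a cancellation, and adds: "Any replacement cycles will be recorded as non-trial treatments".

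The IUI regimen is in section 7.1.1: "letrozole will be commenced at a dose of 5mg (2 tablets) once daily". Section 7.2.1 names no other IUI stimulation drug: "For IUI, letrozole is the chosen medication with the duration of stimulation recorded". The injection in the IUI pathway comes later: "When at least one follicle reaches a diameter of ≥17mm, ovulation triggering using human chorionic gonadotrophins should be administered". The insemination paragraph labels it a trigger, not stimulation: "Single insemination should be planned 24-40 hours post the ovulation trigger injection".

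Three other places show how the term is meant to be used for IUI:

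- Section 7.1.1 (Insemination) says, for centres without a policy of their own, that a cycle with more than two follicles above 15 mm at triggering should be cancelled.
- Section 8.2.2.1 (Pregnancy outcomes) makes cycle cancellation a secondary outcome and gives failure to respond and over-response as its reasons.
- Section 8.2.2.1 (Complications) dates the safety window of a cancelled IUI cycle from ovarian stimulation, while the IVF window runs from the FSH injection.

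**The concern.** The wording of 7.6 suits IVF, where stimulation is injected. A woman in the IUI arm receives no stimulation injection under the protocol regimen. If her cycle is stopped before the trigger, the literal test for cancellation fails, and so does the test for completion.

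Two things depend on the label. The first is the secondary outcome on cancellation and its reason. IVF cycles stopped after a stimulation injection are counted, while the corresponding IUI cycles might not be, so any error falls on one arm. The second is the replacement rule in 7.6, which is written for cancelled cycles: if the first IUI cycle is not cancelled, it is unclear whether a repeat is a non-trial treatment.

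**Working it through.** The plan gives no cancellation figure to reproduce. The check applies the two tests in 7.6 to each kind of IUI cycle.

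| IUI cycle | Stimulation injection? | Insemination? | Status under 7.6 as written | Status elsewhere in the protocol |
|---|---|---|---|---|
| Letrozole taken, no follicle reaches 17 mm, no trigger | No | No | Neither | Cancelled, failure to respond (8.2.2.1) |
| Letrozole taken, over-response, stopped before the trigger | No | No | Neither | Cancelled (7.1.1, 8.2.2.1) |
| Letrozole, trigger, insemination | No | Yes | Complete | Complete |

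Reading the hCG trigger as the stimulation injection does not rescue the first two rows, because those cycles stop before it is given. The over-response row assumes that the decision is made before hCG is injected; the protocol says only that it is made at the time of triggering.

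**Scale.** With no cancellation rate in the protocol, only the weight of one percentage point can be shown. Inputs from section 14.1 and the trial summary:

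- 471 couples per arm, and 10% loss to follow-up, leaving 471 × 0.90 = 423.9.
- IUI cycles per 100 couples: 270 in the costing table with equal success rates, 281.2 in the one at the 10% margin. These are the printed totals. The second is what 6.4% per cycle gives: 100 + 93.6 + 87.6 = 281.2.

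Cycles in the IUI arm:

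- All couples: 471 × 2.70 = 1,272 and 471 × 2.812 = 1,324, so 1% is 12.7 to 13.2 cycles.
- After loss: 423.9 × 2.70 = 1,145 and 423.9 × 2.812 = 1,192, so 1% is 11.4 to 11.9 cycles.

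Each percentage point of IUI cycles stopped before the trigger is therefore about 11 to 13 cycles that the literal definition leaves out. These totals come from an illustrative costing in which every couple without a live birth goes on to the next cycle, so they lean high.

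**What does not move.** The sample size rests on a 28% control rate, a 10% margin, 90% power, a one-sided alpha of 0.025 and 10% loss. None of these involves cycle status. The primary analysis is by intention to treat on live birth and does not use the definition either.

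**The case against.** The best defence is that the meaning is plain. The protocol itself calls an over-response letrozole cycle cancelled, names failure to respond as a reason for cancellation, and promises sites separate guidance on data fields (section 11.2). A site asked for the reason, with failure to respond as an option, is unlikely to leave a letrozole non-responder out. This stands as a limit on the likely size. It does not make the definition correct: 7.6 is the one place that says what cancelled means, and it conflicts with the other sections.

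The two bullets are also not exhaustive for IVF: a cycle with egg collection but no transfer is neither cancelled nor complete. That is true, but such a cycle lies outside cancellation by the stated cut-off. The IUI cycles here stop before the cut-off and still fail the test. The complications section uses a third label, partial, for IUI cycles, but does not define it, so it does not close the gap.

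A reader might go further and infer that the wording decides which couples enter the per-protocol or CACE analysis. The documents do not support this. The adherent population in 7.6 is "receiving three cycles of IUI (or one or two cycles if pregnant from earlier cycles) with no further fertility treatment", and Table 9 likewise counts cycles; neither uses the word cancelled. Section 7.3 says of a withheld over-response cycle that "this will be recorded in the trial as one of the three attempts", although 7.6 as written would not call it cancelled, so the attempt count does not run through the definition. Whether a non-response cycle counts as one of the three is a separate rule that the protocol does not state. Correcting the word injection would not settle it, and it may be left to the SAP.

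**Conclusion.** The concern holds as a drafting error in a stated definition. As written, 7.6 leaves out IUI cycles stopped before the trigger, for either reason, and contradicts sections 7.1.1 and 8.2.2.1. The possible effects are an undercount of the cancellation outcome in the IUI arm only and doubt over whether a repeat of such a cycle is a non-trial replacement.

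The importance is low. Section 14.2 treats all secondary outcomes as exploratory, and the intended meaning can be inferred from other sections. The size cannot be estimated from the protocol and is zero if sites take injection to mean that stimulation has started. The conclusion that the text is wrong is firm; that it will cause miscounting is only possible.

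**What to change.** Reword the cancellation bullet in 7.6: a cycle is cancelled if ovarian stimulation has started (first letrozole dose for IUI, first stimulation injection for IVF) and the cycle is stopped before insemination (IUI) or egg collection (IVF). This matches the start of treatment already used in section 6.4.1 and in the notes to the schedule in section 9.1.

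The cost is one bullet and a note to sites. The sample size, primary outcome and analysis model do not change. The IUI treatment form is not shown, so whether it needs an edit cannot be told. For consistency with 7.3, the sponsor may also state whether an IUI cycle stopped for failure to respond counts as one of the three attempts, but that is a separate clarification and not part of this correction.
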